9.6.2. Follow-up Process for Clarification for Information

For critical data points (e.g., exposure and outcome data), if there are outstanding questions, discrepancies between forms, or missing data, the appropriate HCP will be contacted for clarification. If needed, three subsequent attempts will be made at intervals of approximately 2 weeks. If no further information is obtained, qualified registry staff or the principal investigator/co- investigator will make a logical determination on discrepant information based on the available data. All clarifications and/or changes will be documented and traceable.

9.6.3. Awareness and Retention

9.6.3.1. Awareness Strategy

An active, targeted, multi-pronged awareness campaign will be employed to recruit participants for the registry. The campaign will focus on:

- Pregnant individuals
- Individuals who have a diagnosis of obesity or overweight with at least one weight-related comorbid condition
- Individuals using tirzepatide or other products for weight management
- Obstetric HCPs
- HCPs who are likely to treat patients with diagnoses of obesity or overweight with at least one weight-related comorbid condition
- HCPs who are likely to prescribe tirzepatide or other products for weight management (including, but not limited to, other therapies with GLP-1 RA activity).

As described in Section 7.4.1, non-Hispanic black and Hispanic individuals are at an increased risk of pre-pregnancy obesity compared to non-Hispanic white and Asian individuals; therefore, the sponsor will make efforts to improve enrollment of participants from underrepresented racial and ethnic populations in this study.

Obstetric HCPs and HCPs who are likely to treat patients with obesity may be identified via HCP directories and/or professional associations. If appropriate and/or needed, pregnant individuals, patients who have a diagnosis of obesity or overweight with at least one weight-related comorbidity, and patients using tirzepatide may be identified through patient support groups and external data sources, such as pharmacy/medical claims or electronic medical records. If appropriate, the sponsor's existing infrastructure for distributing tirzepatide and supporting stakeholders may be leveraged to identify HCPs who are known to prescribe tirzepatide and pregnant individuals who have been exposed to tirzepatide.

To start, the primary aim of the registry's awareness strategy will be to recruit individuals exposed to tirzepatide during pregnancy. Once the characteristics of a portion of the tirzepatide-exposed participants are understood, the awareness campaign for the comparator cohort will be tailored to increase comparability of the cohorts. In addition, individuals who were exposed to tirzepatide before (>25 days prior to date of conception [DOC]) but not during pregnancy (<25 days prior to DOC to pregnancy outcome) will be targeted for enrollment into the comparator cohort.

A multi-modal approach will be used to deliver registry education and awareness materials to targeted HCPs and patients. This approach involves direct-to-HCP outreach as well as online and print advertising directed to both HCPs and patients. In addition, stakeholders may be identified and provided with information regarding the registry via telephone through the Medical Information Contact Centre and/or the patient assistance program. Other relevant approaches and/or stakeholders may be implemented, as needed, to deliver registry education and awareness materials.

All strategies around registry awareness campaigns and materials will comply with local laws and regulations.

Direct-to-HCP Outreach

Direct-to-HCP outreach will be achieved by delivering awareness materials to targeted HCPs via email, fax, and/or hardcopy mail. In addition, the sponsor's representatives may provide registry education and recruitment materials to HCPs in person. HCPs will be asked to identify potential registry participants and encourage their participation by speaking to them about the registry and providing them with the patient-directed registry recruitment materials.

Digital Advertising

Information regarding the registry and the registry recruitment materials will also be available online. A registry-specific website will be developed, where all recruitment materials will be available for download. This website will be accessible through the tirzepatide website and discoverable in any internet browser by performing a search related to pregnancy and tirzepatide, tirzepatide, and/or weight management. Information regarding the registry and/or a link to the registry website may also be available on the following websites:

- FDA listing of pregnancy registries on FDA website
- Clinical trials database website
- Society for Maternal-Fetal Medicine listing of registries
- PPD website

A web-based interface compatible with both computers and mobile devices will also be developed to improve information accessibility and enable broader participation. As deemed necessary, online advertisements on social media sites or other relevant websites (e.g., professional association websites or websites commonly visited by pregnant individuals) may be used to direct potential participants to the registry website. Targeted advertisements on web-

based applications frequented by pregnant individuals will be strategically implemented to drive registry awareness.

Print Advertising

Various print materials will also be used to provide information related to the registry and to facilitate recruitment. The tirzepatide prescribing information provides registry information, including contact information (US requirement only). Information related to the registry also may be directed to HCPs via announcements/publications in relevant professional journals/newsletters or presentations/exhibits at relevant professional meetings. As deemed necessary, print advertisements in newspapers or magazines with targeted patients among their readership may be used to direct potential participants to the registry, and recruitment materials may be distributed to locations commonly frequented by targeted patients (e.g., ultrasound clinics, weight-loss centers).

Awareness Materials

In addition to the registry information in the product label, educational materials designed to elicit interest in registry participation will be developed. All messaging will be aligned with the product label and will be balanced to ensure that it does not unintentionally promote the use of tirzepatide for chronic weight management during pregnancy. Materials may include the following:

- An information sheet and/or brochure that will briefly describe the registry purpose and procedures, including the incentives for participation
- Information on how to access the registry web-based/mobile application
- Registration form and sample participant consent form
- Prescribing information
- Participant consent-to-contact card (this card enables the VRCC to contact the potential participant and provide additional information about the registry)

9.6.3.2. Retention Strategy

A retention strategy, facilitated by engaging both the participant and HCP, will seek to minimize the reporting burden on these groups to the extent possible.

The registry staff will serve as the first and single point of communication for both registry participants and HCPs. The specialized staff, many of whom are obstetric nurses, have experience collecting data for observational studies from both patients and research naïve HCPs. They are experts at developing a rapport with HCPs and participants to facilitate data collection and build one-on-one relationships that will promote retention and reduce overall loss to follow up. To promote HCP engagement, status updates may be shared with HCPs through various means (i.e., email, newsletters, and the registry website). Materials provided will emphasize the mission of the registry to promote participant engagement and point participants to the website.

The registry will use streamlined data collection processes and simple, concise data collection forms that focus on specified outcomes to reduce the burden of reporting. The registry will provide multiple options for communication and data submission (e.g., phone, fax, mail, email,

website, web based/mobile application) and a flexible follow-up schedule to enhance retention and maximize data reporting. The registry will also attempt to collect contact information of family members or friends in case the participant cannot be reached, which can further promote retention. Finally, in countries where local guidelines permit, the registry will provide stipends to participants (at enrollment and at the end of data collection) and their HCPs who serve as data reporters (once all data have been collected and all queries have been resolved).

Assessment of Recruitment and Retention

Participant recruitment and retention are the greatest challenges experienced with pregnancy registries. Recruitment largely depends on a strong awareness campaign and product use or uptake in the market. It is important to note that low recruitment/enrollment in pregnancy registries may be due to limited use of the product, especially when the product is new to the market. Pregnancy registries typically enroll only a small fraction of all exposed pregnancies, regardless of awareness strategies employed.

To maximize recruitment and retention, the registry's recruitment and retention strategies will be flexible and will be continuously assessed. The registry will assess recruitment and retention by collecting information from reporters (i.e., HCPs and participating individuals) on the sources from which they received information about the registry (recruitment) and the reasons for which they ceased participation or were lost to follow-up (retention). Based on these assessments, the registry's recruitment and retention strategies will be adjusted to maximize registry participation. The registry's Scientific Advisory Committee (SAC) will also be consulted regarding recruitment and retention strategies.

9.6.4. Participant Registration

Pregnant individuals who are interested in providing data to the registry and participating in the registry may self-enroll through the web-based application or by calling the VRCC. To enroll, each individual will answer a series of screening questions to assess their eligibility, and, if eligible, they will be asked to provide informed consent, their primary contact information, alternate contact information for a family member or friend, contact information for HCPs who are/will be involved in their care or the care of their infant, and medical releases to allow these HCPs to provide data to the registry. To allow for full follow-up on all enrolled pregnant individuals and their infants prior to study end, the last participant will be enrolled on or before 31 December 2033.

9.6.5. Assessments for Safety

The registry is strictly observational; office visits and all treatment regimens will be determined by HCPs. No additional laboratory tests or HCP assessments will be required as part of this registry. Refer to Section 10 for reporting of adverse events (AEs) and other safety information.

9.7. Variables

9.7.1. Exposure Definitions and Ascertainment

Exposure to tirzepatide is a condition for inclusion into the exposed cohort. Exposure is defined as bodily uptake of any dose of tirzepatide at any time during pregnancy (from conception to pregnancy outcome) or prior to pregnancy (within a specified time based on the product's half-life). Due to the half-life of tirzepatide (approximately 5 days), tirzepatide is likely to be eliminated from the body within 5 half-lives (25 days or 3.5 weeks). Therefore, individuals exposed to tirzepatide within ≤ 25 days of DOC will be considered exposed. Individuals in the tirzepatide cohort who are exposed to other GLP-1 RA therapies during pregnancy or within 5 times the half-life of the drug prior to conception will be excluded from the main analysis to prevent class effect interactions. However, they may still be enrolled into the study as part of the tirzepatide exposed cohort.

Exposure to comparator products for weight management is defined as bodily uptake of any dose of a qualifying product for weight management at any time during pregnancy (from conception to pregnancy outcome) or prior to pregnancy (within 5-half-lives of DOC). Detailed information on drugs for weight management and their respective exposure windows are detailed in Drugs of Interest for Cohort Eligibility.

Detailed information on dose, route, frequency, dates/duration of exposure, and indication/reason for use will be collected, and exposure will be further categorized by earliest trimester of exposure. Section 9.7.5 provides information on the methods used to determine gestational age and trimester of exposure.

Exposure information will be updated at each pregnancy follow-up and changing exposures will be accounted for in the analysis. For example, if a pregnant individual was enrolled into the comparator cohort but later during pregnancy became exposed to tirzepatide, for the analysis they would be included in the tirzepatide exposed cohort.

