DOC, defined as 2^{0/7} gestational weeks, will be calculated as first day of LMP plus 14 days (2 weeks).

If EDD is not reported by the HCP but LMP data are available, the registry will use first day of LMP to calculate EDD, gestational age, and DOC.

Individuals will be considered exposed during pregnancy if the exposure occurs any time from 25 days prior to the DOC to the pregnancy outcome. For the analysis of MCM, first trimester exposure will be defined as exposure from 5 times the product's half-life (i.e., 25 days for tirzepatide) prior to the DOC to 13^{6/7} gestational weeks.

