9.11.2. Statistical Methods

Registry data will be summarized in tables and listings by study cohort, as appropriate. These data include maternal demographic characteristics and pre-pregnancy anthropometrics, pregnancy information, maternal obstetrical history, family history of congenital malformations, disease information, maternal exposures during pregnancy, pregnancy outcome information (including gestational age of outcome), and infant outcome information.

For each continuous variable, the number of observations, median, mean, standard deviation, minimum, and maximum will be reported. For each categorical variable, the frequency and percentage in each category will be reported. The frequency and percentage of participants with missing data for each data point will be presented. Results will be rounded to one decimal place; therefore, percentages may not always add up to 100.

Pair-wise comparisons of demographic and baseline characteristics and event rates of the outcomes of interest will be conducted between the study cohorts, as follows:

- Comparison #1: Tirzepatide exposed cohort vs. AOM active comparator cohort

- Comparison #2: Tirzepatide exposed cohort* vs. AOM unexposed comparator cohort
*Comparison #2 will include a subset of tirzepatide exposed cohort who have obesity or are overweight with at least one weight-related comorbid condition at the time of conception so as to improve comparability to AOM unexposed comparator cohort with the same obesity-related eligibility criteria.

For the analysis, participants from all countries will be pooled. Comparisons will be conducted using the methods described below, and p-values and 95% confidence intervals will be reported, as appropriate, to reflect statistical uncertainty. All outcomes will be analyzed as binary variables. The study is not powered for multiple comparisons; thus, p-values associated with secondary or exploratory outcomes will be nominal.

In addition, the prevalence of the outcomes in the general population and/or populations of individuals overweight or with obesity, from the literature, will be used to put the registry-observed outcome prevalences into context.

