9.11.2.1. Analysis of Primary Outcome

Prevalence of the primary outcome will be calculated according to the conventions described in [Table 9.6](#). In general, prevalence will be calculated by dividing the number of cases with an MCM by the appropriate denominator. Prevalence is preferred over incidence when examining pregnancy outcomes, such as congenital malformations, because incidence cannot be reliably estimated given the complexities in the reproductive process.⁹⁷

For MCM, prevalence in the exposed cohort will be calculated among the subset of individuals who are exposed during the first trimester. For the primary analysis, prevalence will be calculated among live births, and a secondary analysis will be conducted among live births and fetal losses ([Table 9.6](#)).

The unweighted univariate regression will be used to compare the crude (unadjusted) relative risks (RRs) of MCM in the tirzepatide exposed and each of the comparator groups, respectively: tirzepatide exposed vs. AOM active comparator and tirzepatide exposed vs. AOM unexposed comparator.

Adjusted methods will incorporate weights estimated using the inverse probability of treatment weighting (IPTW) method to balance the cohorts regarding observable covariates. A weighted generalized linear model using a binomial family and a log (RR) link with robust sandwich variance estimation or a modified Poisson regression⁹⁸ with robust error variance will be employed to estimate an adjusted RR. As with the unweighted analysis, two sets of comparisons will be conducted separately: tirzepatide vs. AOM active comparator and tirzepatide vs. AOM unexposed comparator.

The adjusted comparison of the overall prevalence of MCM observed in the tirzepatide exposed and the comparator cohorts will be considered the primary analysis. A p-value <0.05 will be considered statistically significant.

Table 9.6. Calculation of Primary Outcome Prevalence

Outcome	Numerator	Denominator
Primary analysis: among live births	Live births with confirmed (by adjudication) MCMs (excluding MCMs not known to be associated with medication exposure ^a) among individuals with pregnancy outcome data and, if applicable, exposure during 1 st trimester	Live births among individuals with pregnancy outcome data and, if applicable, ^b exposure during 1 st trimester

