Secondary analysis: among all pregnancy outcomes	Live births and fetal losses ^c with confirmed (by adjudication) MCMs (excluding MCMs not known to be associated with medication exposure ^a) among individuals with pregnancy outcome data and, if applicable, exposure during 1 st trimester	Live births and fetal losses ^c among individuals with pregnancy outcome data and, if applicable, exposure during 1 st trimester

Abbreviation: MCM = major congenital malformation.

^a To avoid misattribution of the malformation to the medication, MCMs not known to be associated with medication exposure such as chromosomal abnormalities, genetic syndromes, fetal alcohol syndrome, prematurity-related conditions in infants born at <36 gestational weeks (e.g., patent ductus arteriosus, patent foramen ovale, inguinal hernias, or undescended testes), and positional effects (e.g., hip dislocation due to breech position or abnormal skull shape due to crowding by multiple fetuses) will not be considered MCMs in the statistical analyses comparing MCM prevalence between the cohorts.⁵¹

^b Exposure during first trimester applicable only for exposed cohorts.

^c Fetal losses include stillbirths, SABs, and induced abortions.

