9.11.2.2. Analysis of Secondary and Exploratory Outcomes

Prevalence of the secondary and exploratory outcomes will be calculated according to the conventions described in [Table 9.7](#). In general, the prevalence of each outcome will be calculated by dividing the number of cases of the outcome by the appropriate denominator for that particular outcome, based on clinical knowledge.

Table 9.7. Calculation of Secondary and Exploratory Outcome Prevalence

Outcome [Exposure window]	Numerator	Denominator
Secondary outcomes		
Maternal pregnancy complications		
Gestational diabetes [Exposure: Any trimester]	Individuals with gestational diabetes	Individuals included in the analysis population
Sensitivity analysis: Gestational diabetes	Gestational diabetes among pregnancies with pregnancy outcome data	Individuals with pregnancy outcome data
Pregnancy-induced hypertension [Exposure: Any trimester]	Individuals with pregnancy-induced hypertension	Individuals with pregnancy of 20 gestational weeks or more
Sensitivity analysis: Pregnancy-induced hypertension	Pregnancy-induced hypertension among pregnancies with pregnancy outcome data	Individuals with pregnancy of 20 gestational weeks or more with pregnancy outcome data
Pre-eclampsia [Exposure: Any trimester]	Individuals with pre-eclampsia	Individuals with pregnancy of 20 gestational weeks or more
Sensitivity analysis: Pre-eclampsia	Pre-eclampsia among individuals with pregnancy outcome data	Individuals with pregnancy of 20 gestational weeks or more and with pregnancy outcome data
Eclampsia [Exposure: Any trimester]	Individuals with eclampsia	Individuals with pregnancy of 20 gestational weeks or more
Sensitivity analysis: Eclampsia	Eclampsia among individuals with pregnancy outcome data	Individuals with pregnancy of 20 gestational weeks or more with pregnancy outcome data
Fetal Outcomes		
SAB [Exposure: DOC to $\leq 19^{6/7}$ gestational weeks]	SABs among individuals with pregnancy outcome data who are enrolled (and exposed, if applicable) prior to 20 gestational weeks	Individuals with pregnancy outcome data who are enrolled (and exposed, if applicable) prior to 20 gestational weeks
Induced abortion [Exposure: Any trimester]	Individuals with pregnancy ending in induced abortions	Individuals included in the analysis population
Sensitivity analysis: Induced abortion	Induced abortions among individuals with pregnancy outcome data	Individuals with pregnancy outcome data

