As described in Section 9.11.2, prevalence of the outcomes among the tirzepatide exposed cohort will be compared with each of the two comparator cohorts. The adjusted comparison of the prevalence of MCM observed in the tirzepatide exposed relative to the unexposed comparator cohorts will be considered the primary analysis. Because participants who seek and receive pharmacotherapy for weight management may have greater disease severity, confounding by indication (also known as channeling bias) will need to be carefully considered for the comparison. Confounding by indication can occur when participant characteristics, such as disease severity, affect prescribing patterns. If not accounted for in the analysis, such confounding could result in an apparent increased risk of the outcomes associated with medication use. To minimize the impact of potential confounders, the registry will record the characteristics of individuals in both exposed and unexposed comparator cohorts and use statistical methods to examine and account for any differences between cohorts in the analysis. The registry will employ identical data collection and follow-up procedures across the registry cohorts to minimize any potential bias. As is described in Section 9.11.2, this study will employ the IPW method to address the imbalance between cohorts. Although statistical methods will be used to account for confounding or mediating variables, it may not be possible to control for all variables (e.g., unknown) that could influence the results of the study. Therefore, some important confounders (either measured or not) could still be unbalanced.

Since the registry is focused on prospective enrollment, misclassification of drug exposure is non-differential regarding outcome. However, outcome misclassification could occur, especially regarding minor congenital malformations that may be overlooked or unreported. Although some MCMs may not be easily visible at birth, most will be apparent by 12 months of age, so misclassification of these outcomes is expected to be minimal in this registry, which aims to follow infants through 12 months of age.

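### Comparators who start tirzepatide later in pregnancy are moved whole into the exposed cohort, and no rule requires the first dose to precede the outcome (secondary and exploratory outcomes)

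*Protocol*

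**What the plan says.** Section 9.7.1 states the principle: "Exposure information will be updated at each pregnancy follow-up and changing exposures will be accounted for in the analysis". Its only worked example is a comparator who "later during pregnancy became exposed to tirzepatide, for the analysis they would be included in the tirzepatide exposed cohort". Table 9.1 (section 9.5.2) supplies the other half, because tirzepatide exposure at any point in pregnancy excludes a person from both comparator cohorts.

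Section 9.11.2 adds: "All outcomes will be analyzed as binary variables". Table 9.7 attaches an exposure window to each outcome, and most are of the form "Gestational diabetes [Exposure: Any trimester]". The same window applies to pregnancy-induced hypertension, pre-eclampsia, eclampsia, induced abortion, stillbirth, minor malformations, hyperemesis and maternal cardiac disease. Spontaneous abortion requires exposure before 20 weeks, and preterm birth before 37 weeks.

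Major malformations (MCM) are treated differently: "For MCM, prevalence in the exposed cohort will be calculated among the subset of individuals who are exposed during the first trimester". The note to Table 9.6 reads "Exposure during first trimester applicable only for exposed cohorts".

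**The concern.** Cohort membership is decided by something that happens after follow-up has begun. That can do two kinds of damage, on different outcomes.

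- **Event before dose.** A comparator diagnosed with hyperemesis or gestational diabetes who later takes tirzepatide for weight management becomes an exposed case, and the comparator cohort loses that case. The relative risk (RR) is pushed up.
- **Event-free time before dose.** To start tirzepatide in week 33, a participant must still be pregnant in week 33. Her earlier weeks without a loss or delivery are credited to the drug. The RR is pushed down.

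Weighting on baseline covariates (section 9.11.2.4) cannot correct assignment by a later event. The subgroup by earliest trimester of exposure (section 9.11.2.5) depends on sample size and leaves the main RR as it is. In a required safety study, a false signal and false reassurance both matter.

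**Working it through.** **1. Which outcomes are affected.** Setting the section 9.7.1 rule against each outcome's window:

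| Outcome | Effect of the rule |
|---|---|
| Gestational diabetes, pregnancy-induced hypertension, pre-eclampsia, eclampsia, hyperemesis, cardiac disease, minor malformations | Events arising before the first dose can count as exposed |
| Spontaneous abortion, induced abortion, stillbirth, preterm birth | The event ends the pregnancy, so no dose can follow it; event-free time before the dose is credited to tirzepatide |
| MCM | Exposed set limited to first-trimester exposure; a comparator starting after 13 6/7 weeks leaves both arms |
| SGA, LGA, postnatal outcomes | Determined at or after birth; neither problem arises in this form |

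Stillbirth is defined from 20 weeks (Table 9.3), so a week-33 starter brings at most 33 − 20 = 13 weeks at risk. Section 9.11.2.2 censors spontaneous abortion at 20 weeks and preterm birth at 37 weeks. That closes the window at the end but does not start risk time at the first dose.

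**2. The plan's own figures.** The Walters approximation for 3% against 9% gives 265 live births per cohort (power 80.1%). Enrollment is 265/0.9³ = 363.5, so 364 per cohort and 1,092 in total. All three figures reproduce.

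**3. Gestational diabetes, true RR = 1.** The reference prevalence in Table 9.4 is 6.9%, and 0.069 × 364 ≈ 25 cases per cohort. Let k comparators start tirzepatide after diagnosis. The value of k is an assumption.

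- Moved to the exposed cohort: RR = [(25+k)/(364+k)] / [(25−k)/(364−k)]
- Only lost from the comparator: RR = (25/364) / [(25−k)/(364−k)]

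| k | Moved | Only lost |
|---|---|---|
| 2 | (27/366)/(23/362) = 1.16 | 1.08 |
| 3 | (28/367)/(22/361) = 1.25 | 1.13 |
| 5 | (30/369)/(20/359) = 1.46 | 1.23 |

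The last column applies when the drug is started for a reason other than weight management. Section 9.11.1.1.2 then keeps the participant out of the main analysis, but she has still left the comparator.

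**4. The same bias by switching share.** Let a share f of the exposed cohort be switchers whose risk of the complication is m times baseline. Then RR = 1 + f(m − 1). For m = 2 to 3 this gives 1.01–1.02 (f = 1%), 1.05–1.10 (5%), 1.10–1.20 (10%) and 1.20–1.40 (20%).

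**5. Spontaneous abortion, true RR = 1.** Assume 11.8% risk (Table 9.4), a constant hazard from entry at week 8 to week 20, and a switch at week 14. Comparator risk is held at 11.8%. The weekly hazard is −ln(0.882)/12 = 0.0105, so a switcher's remaining risk is 1 − exp(−6 × 0.0105) ≈ 6.1%. With RR = [(1−f) × 0.118 + f × 0.061]/0.118:

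| f | RR | Range, entry weeks 6–10 and switch weeks 12–18 |
|---|---|---|
| 1% | 0.995 | 0.992–0.998 |
| 5% | 0.976 | 0.958–0.990 |
| 10% | 0.952 | 0.915–0.981 |
| 20% | 0.903 | 0.830–0.962 |

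**The case against.** **Few participants will switch.** This is the strongest reply, and it stands. Section 7.4.3 says patients are advised to discontinue when pregnancy is recognized, and section 9.9.2 assumes 95% discontinuation. A comparator in the main analysis would have to start after her pregnancy was known. In the gestational diabetes illustration, k = 2 to 5 means that 8% to 20% of the 25 comparator cases start the drug after diagnosis, which is a lot. A reader might take the planning assumption of 90% first-trimester exposure (section 9.9.1) to mean about 36 switchers among 364. It does not: someone first dosed in the second trimester who enrolls afterwards was never a comparator.

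**The primary analysis is protected.** A reader might infer that the rule distorts every outcome, MCM included. Section 9.7.5 answers most of that: "For the analysis of MCM, first trimester exposure will be defined as exposure from 5 times the product's half-life" before conception to 13 6/7 weeks, so a later starter cannot enter the exposed MCM set. What remains is her loss from both arms. This biases the MCM RR only if switching is related to malformation, for example after a prenatal finding, and the protocol shows no such link.

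**Section 9.13 on misclassification.** A reader might think the rule refutes the statement that "misclassification of drug exposure is non-differential regarding outcome". It does not. That sentence concerns wrongly recorded exposure, whereas here the dose may be recorded correctly and the question is its timing. For the same reason, the sentence gives no reassurance on this point.

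**The statistical analysis plan may handle it.** It may refine the analysis, but the protocol already fixes the handling by example, and the example is whole-person reassignment.

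**Conclusion.** The point holds for the maternal complications, minor malformations, pregnancy losses and preterm birth. The protocol reassigns later starters as whole persons and neither requires the dose to come first nor starts risk time at the dose. For MCM, only the loss of late-starting comparators from both arms remains.

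The size is unknown, because no switching share is given, and it is probably small. At a 1% share the distortion is 1% to 2% for complications and under 1% for spontaneous abortion. It becomes material only at shares of 10% or more, or if several comparators start after a diagnosis. The direction differs by outcome. The outcomes with quantified bias are secondary or exploratory, with nominal p-values. It should be fixed, but it does not threaten the primary analysis.

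**What to change.** Replace the example in section 9.7.1 and align Tables 9.1 and 9.7 with it. Changing section 9.7.1 alone would leave Table 9.1 excluding the same participants from the comparators.

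1. **MCM and minor malformations:** set the cohort by exposure status through 13 6/7 weeks. Later starters stay in their enrolled comparator cohort.
2. **Maternal complications:** count a participant as tirzepatide-exposed only if her first dose precedes the diagnosis; if the diagnosis came first, she stays in her enrolled cohort. The text must also place later starters who are never diagnosed, since moving only them would credit their event-free time to the drug. Rule 3 avoids this and needs no diagnosis date.
3. **Spontaneous abortion, induced abortion, stillbirth and preterm birth:** set the cohort by exposure status at enrollment, keep later starters there, and describe them separately. Censoring at the first dose is not a substitute, because it has no defined meaning in a binary RR model.

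Report the reassignment as now written as a sensitivity analysis.

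**Cost.** Dose dates are already collected. Section 9.8 lists the maternal complications without an onset date, although section 9.11.2.8 refers to start dates of conditions. One date field per complication may therefore be needed, and it should be confirmed early because unrecorded dates may not be recoverable. Some comparators will carry late tirzepatide exposure, which slightly dilutes the contrast. The figures of 265 and 364 do not change.
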